Based on our current study, we anticipate that most of our participants will be on probation rather than parole. However, confidentiality issues will be stressed during informed consent and will include the description of a federal Certificate of Confidentiality. Participants will also be assured that their screening results, HIV/HCV test results, study participation, and study data will not be made available to any representative of the jail or criminal justice system. Jail officials and administrators will not be informed of participants who participate in the screening, eligibility data, or refusals in order to protect participant confidentiality. Consent form language reflects this emphasis on participant confidentiality.

Condition 5. For studies that require follow-up, provisions are made including consideration for the length of individual sentences; informed consent must reflect provisions for follow-up.

Describe what provisions have been made for follow-up and how this information will be relayed to the prisoner participants:

For this pilot study, follow-up data will be collected 3 months post-release from jail to assess feasibility and acceptability of the FB intervention, as well as self-report measures at 3 months to assess ratings of acceptability and feedback. In addition, measures are proposed for field testing during the 3 month follow-up to examine relevant covariates and participant characteristics which may influence intervention behavioral outcomes, as well as to examine integrity of our randomization procedures. To achieve a high follow-up rate, participants will also be asked to provide telephone numbers of the person who is most likely to know where they will be when they are released (usually a mother or grandmother). Locator information will also include Facebook, primary and secondary addresses, telephone numbers, hangouts, aliases, and contact information for close relatives, and friends. Once located, follow-up interviews will be face-to-face and will be conducted at a location mutually agreed upon by participants and the study coordinator. Participants will be informed about follow-up interviews and time intervals at the baseline interview, and they will be provided with incentives for completed interviews.

Condition 6. Information about the study is presented in a language understandable to prisoners.

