- For each source or method described, please list or attach all data to be collected (such as genetic information, interview scripts, survey tools, data collection forms for existing data, etc.).
- If you will conduct a record or chart review, list the beginning and end dates of the records you will view.

Primary outcomes of interest for this R34 developmental trial include feasibility and acceptability of our methods and intervention delivery as measured the 3-month follow-up interview following jail release (see Table 3, bottom of page 8 of the Research Strategy). Measures assessing feasibility and acceptability will be collected via secondary data analysis of the FB site at 3 months post-release (number initiating FB site, number of posts viewed, length of engagement, likes/shares, etc), as well as through self-report during the 3 month follow-up (usability of the site, acceptability of the site). In addition, measures are proposed for field testing at the baseline and 3 month interviews to examine relevant covariates and participant characteristics which may influence intervention behavioral outcomes, as well as to examine integrity of our randomization procedures. These measures include demographics (age, race, marital status, employment, education); substance use severity measured by the NM-ASSIST, injection drug use and sharing practices as measured by the Risk Behavioral Assessment for Women, risky sexual practices including unprotected sex and sex exchange as measured by the RBA-Women, mental health issues related to depression, anxiety, and/or trauma, and involvement in high-risk social networks. See attached for DRAFT measures, which is still under development.

Attachments

| Attach Type | File Name |
|----------------|--|
| DataCollection | Rural Women Social Media 3 Month Follow Up Codebook 5-26-20-Marked.pdf |

| | |
|----------------|--|
| DataCollection | rural women grant Codebook.pdf |
| DataCollection | Appendix 3 Adult Case Report Form 2018_508.pdf |
| DataCollection | Appendix 4 Risk Factor Ascertainment.pdf |
| DataCollection | Appendix 6 Payment Receipt.pdf |
| DataCollection | Appendix 7 W9.pdf |
| DataCollection | Appendix 8 Institution Payment Receipt.pdf |
| DataCollection | Baseline Codebook 5 16 19 clean.pdf |
| DataCollection | FB Locator Form.pdf |
| DataCollection | FB Screener.pdf |
| DataCollection | HIV HCV Testing Forms.pdf |
| DataCollection | Facebook Data Collection Form_v2.pdf |

Resources

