be kept separate from the actual participant data. (7) All identifying information (consents, locator forms, payment forms) will be kept locked at all times. (8) All documentation of IRB approval including OHRP certification for prisoner research, original consents, Certificate of Confidentiality, human participants certification for staff, and other related study information will be filed and easily accessible to the PI and the Research Coordinator.

Additional data safety and monitoring procedures at the University of Kentucky Center on Drug and Alcohol Research include: (1) All staff must successfully complete the Protecting Study Volunteers in Research Certification or the CITI on-line human subjects training course. (2) Specific and clear protocols for adverse events and violations of study protocols are established. (3) Data reports including recruitment and interview reports, contact and tracking reports, no show/refusal reports, and session contacts will be prepared on a regular basis.

Any data collected in a jail will be secured in a lock box during transport. All identifying information (consents, locator forms, payment forms) will be kept locked at all times in file cabinets in the office of the Principal Investigator at the University of Kentucky Center on Drug & Alcohol Research. Each participant will receive a unique identifying number. All research data collection instruments will be identified by this number only. The master list matching identifiers to specific participants will also be maintained in a locked file in the PI's office. Research data will be reported in aggregate form only. Computer files will be retained, but computerized identifying information will be destroyed when data collection and file building is completed. Participants will not be identified by name in analytic data files. All documentation of IRB approval including OHRP certification for prisoner research, original consents, Certificate of Confidentiality, human participants certification for staff, and other related study information will be filed and easily accessible to the PI and the Research Coordinator.

[Back to Top](#)

Future Use and Sharing of Research Data

If the results of this study will be used by members of the research team or shared with other researchers for future studies, please address the following:

- list the biological specimens and/or information that will be kept

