Primary outcomes and data analysis are anchored in Aim 2 of this R34 application to feasibility test an evidence-based intervention for Facebook delivery as an innovative approach to increasing access to prevention resources for high-risk rural women during community re-entry. According to the seminal work by Leon and colleagues (2011), pilot studies such as the one proposed here do not generally require extensive sample size calculations, and it is recognized that “effects” generated from pilot studies cannot be utilized to power the eventual larger trial due to the wide confidence intervals often obtained in small pilots (Leon et al., 2011; Thanbane et al., 2010). In this R34 application, our goal is not to conduct a fully-powered trial to detect significant differences in risk behavior based on the intervention; but rather a pilot study with “a sample size based on the pragmatics of recruitment and the necessities for examining feasibility” (Leon et al., 2011; p. 627).

Our proposed sample size was guided by several considerations. The target jail study sites have a combined daily average census of approximately 253 women. Based on our current trial, 90% are anticipated to meet the substance use criteria for the study (n=228), and 60% of those are expected to be regular Facebook users, for a possible daily population of 160 women. Based on recommendations for sample size considerations in pilot and feasibility studies (Moore et al., 2011; Thabane, et al., 2010), we based our planned sample size on the confidence intervals for number of participants needed to assess participation rate, a key aspect of feasibility. Previous Facebook intervention trials have demonstrated high participation rates ranging from 80%-95% (Naslund, et al., 2017; Young et al., 2013). With a confidence interval width of 10% and a population of 160, the proposed sample size of 60 participants will be sufficient to examine feasibility and acceptability of the NIDA Standard using Facebook (n=30) compared to re-entry services as usual (n=30) in this R34 pilot trial.

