Descriptive statistics (frequencies and means) will be used to characterize the participants and describe feasibility indicators (e.g., proportion of women agreeing to enroll in the study, the number of participants who “friend” the closed study site, the number of posts viewed on the study site, length of time of engagement). Based on other Facebook trials and our previous work (e.g., Dickson et al., 2017; Young et al., 2013), the participation rate is expected to be high (90%) across these variables. Among participants who use Facebook in the proposed trial, acceptability of intervention delivery is also expected to be high as measured through engagement (“likes”, “shares”, etc), changes in HIV/HCV knowledge, and connections with new “friends”. In addition, bivariate analyses (e.g., chi square tests, independent groups t-tests, and other parametric and

non-parametric analyses, as appropriate) will be used to examine potential differences in other covariates of interest (risky drug use and sexual practices) between the two study conditions.

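### The sample size paragraph claims a comparison with usual services that no named feasibility indicator can supply after randomisation, and 3-month completion by arm is not a named indicator

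*Combined protocol and SAP*

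**What the plan says.** The sample size paragraph of Data Analysis bases the number of women on "confidence intervals for number of participants needed to assess participation rate, a key aspect of feasibility". Taking 160 as the population and 10% as the interval width, it concludes that 60 women are "sufficient to examine feasibility and acceptability of the NIDA Standard using Facebook (n=30) compared to re-entry services as usual (n=30" women).

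The next paragraph of Data Analysis gives examples of feasibility indicators. The first is "proportion of women agreeing to enroll in the study"; the others are joining the closed site as a friend, posts viewed, and length of engagement. Acceptability is to be judged, among participants who use Facebook in the trial, by likes and shares, change in HIV/HCV knowledge, and new friend connections. Data Collection & Research Materials adds site initiation and self-reported usability and acceptability of the site. Under Potential Risks & Benefits, the site admits only women whom the study has invited.

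The one between-arm analysis described is a set of bivariate tests on risky drug use and sexual practices.

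Data Collection & Research Materials puts "feasibility and acceptability of our methods and intervention delivery" in the primary outcome. Follow-up is treated as important elsewhere. Condition 5 of the Prisoners section says: "To achieve a high follow-up rate, participants will also be asked to provide telephone numbers". Payment offers a bonus for completing both interviews. Data and Safety Monitoring lists "contact and tracking reports, no show/refusal reports" among its routine reports. Data Analysis names no follow-up completion rate, overall or by arm.

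**The concern.** A comparison between arms needs a quantity that can be observed in both. The sample size paragraph claims one for feasibility and acceptability, but the indicators that follow are mostly about the Facebook site. A reader who takes the sentence at face value will expect a 30 versus 30 contrast, or estimates on 60 women, and for these measures will get neither.

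Two things are at stake. First, the precision of the main feasibility figures is that of 30 women, and the text does not say so. Second, the pilot is meant to inform a larger trial. Retention in each arm is a basic input to that design, and it also shows how far the planned risk-behaviour comparison can be read, because only women interviewed at 3 months contribute 3-month data to it. As written, the plan does not commit to reporting it.

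**Working it through.** **The plan's own figure.** Inputs from Data Analysis: interval width 10%, population 160, earlier participation rates 80% to 95%, expected rate 90%. The confidence level is not stated, nor whether 10% is the half or the full width. For a single proportion with finite population correction, n0 = z²p(1−p)/h² and n = n0/(1 + (n0−1)/N).

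- 95% confidence, p = 0.5, half-width 0.10, N = 160: n0 = 3.8416 × 0.25/0.01 = 96.04; n = 96.04/(1 + 95.04/160) = 60.2, or 61 rounded up. This matches 60.
- 90% confidence, p = 0.9, full width 0.10 also gives 61.
- At 95% confidence the plan's own rates do not give 60. With half-width 0.10, n is 45, 29 and 17 at 80%, 90% and 95%. With full width 0.10, n is 98, 75 and 51.

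On either matching reading, the formula treats the women as one sample estimating one rate. It has no between-arm term, so the sample size does not supply the comparison.

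**Which indicators can be seen in which arm.**

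| Indicator | Facebook arm | Usual services arm |
|---|---|---|
| Agreement to enrol | before randomisation | before randomisation |
| Site initiation or friending, posts viewed, length of engagement | yes | no, site closed |
| Likes and shares; usability and acceptability of the site | yes | no |
| New friend connections | yes | unclear |
| Change in HIV/HCV knowledge | yes | possible; no comparison planned |
| Risky drug use and sexual practices (not a feasibility measure) | yes | yes, compared |
| 3-month interview completed (not a named indicator) | yes | yes |

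No row that the plan names as a feasibility indicator offers a between-arm comparison after randomisation.

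**Precision on 30 women.** Exact (Clopper-Pearson) 95% intervals:

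- 27/30 (the plan's expected 90%): 73.5% to 97.9%.
- 24/30 (80%, the low end of the cited range): 61.4% to 92.3%.
- For contrast, 54/60 gives 79.5% to 96.2%.

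The normal half-width on 30 is 1.96 × √(0.9 × 0.1/30) = 10.7 points at 90%, and 14.3 points at 80%. With the plan's finite population correction these become 9.7 and 12.9. If 10% was meant as a half-width, 30 women just meet it at 90% with the correction, and do not at 80%.

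**Precision of completion by arm.** With 30 per arm and the same rate p in both, the 95% half-width of the difference is 1.96 × √(2p(1−p)/30):

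- p = 0.90: 15.2 points
- p = 0.85: 18.1 points
- p = 0.80: 20.2 points

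The plan gives no follow-up rate, so these values of p are assumptions. A difference with this interval is descriptive and is no basis for a test.

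**The case against.** The best defence is that the clause is a loose description of the 30/30 allocation and not an analysis plan. Objectives defines the primary outcome as feasibility and acceptability of the delivery methods, Data Analysis plans descriptive statistics for it, and no between-arm feasibility test is promised. The pilot also disclaims power to detect differences in risk behaviour. The indicator lists are openly illustrative, and Data Collection & Research Materials refers to a Table 3 of the Research Strategy that is not in the document. This defence limits the point to what the available text names and makes it one of wording and reporting. It does not rescue the sentence, which still says the sample suffices for a comparison that no named feasibility indicator can supply. An open-ended list also commits nobody to report completion by arm.

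A reader might go further in three ways that the documents do not support.

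- That the usual services arm has no listed indicator, or adds nothing to the primary outcome. HIV/HCV knowledge could be measured there. The plan also examines the integrity of randomisation, which needs both arms and bears on the feasibility of the methods. The restriction of acceptability to participants who use Facebook is itself ambiguous, since prior Facebook use is an entry criterion for everyone.
- That follow-up completion is the only measure the arms share. Substance use, injection and sexual risk measures are planned at both interviews, and HIV/HCV testing is offered at all of them.
- That follow-up will differ by arm and bias the risk-behaviour comparison. This is possible, because only one arm has contact through the site, but no document gives arm-specific rates. Condition 5 collects locator details, including Facebook, without distinction by arm, and Research Procedures allows mailed reminders.

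**Conclusion.** The point holds within limits. The comparison with usual services is unsupported for site use and site acceptability; those are single-arm estimates on 30 women, with an exact 95% interval of about 73% to 98% at the expected 90%. HIV/HCV knowledge is the acceptability measure that clearly could be compared, provided it is collected in both arms; Data Collection & Research Materials does not name it among the interview measures. Completion of the 3-month interview by arm is absent from the named indicators, although a high follow-up rate is a stated goal and feasibility of the study's methods is part of the primary outcome. Whether retention will in fact differ cannot be judged from the document; reporting it would show. These conclusions assume 30 women per arm, as the plan states, and that the material not in the document adds no by-arm completion indicator. The change should be made: it is inexpensive, and it corrects what the plan says its sample size delivers.

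**What to change.** - **Data Analysis, sample size paragraph.** Remove the comparison with usual services for site-use and site-acceptability measures. State that these are single-arm estimates on 30 women, and give the exact 95% interval to expect. Keep HIV/HCV knowledge as a descriptive between-arm comparison if it is measured in both arms.
- **Data Analysis, descriptive statistics paragraph.** Add completion of the 3-month interview (yes/no), among all women randomised, by arm, with the difference and its 95% interval, as a descriptive feasibility indicator.
- **Beside the risk-behaviour comparison.** Show baseline characteristics of women found and not found at 3 months, by arm.

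Cost: one more feasibility indicator, which is an addition to the outcomes and should be recorded as such, and a less favourable statement of what 60 women deliver. No new assessment is needed, because completion follows from matching the randomisation list to the completed interviews. The routine tracking reports may help, but the document does not say that they are kept by arm or cover every woman randomised, so that should be confirmed.
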